## 1.2 Study design

This is a Phase IV, multicenter, randomized, double-blind, placebo-controlled, parallel-group study evaluating the effect of Acclidinium Bromide (a long-acting muscarinic antagonist delivered by the Pressair® dry powder inhalation [DPI] device) compared with placebo on long-term CV safety and COPD exacerbations in outpatients at least 40 years of age who have been diagnosed with moderate to very severe COPD (postbronchodilator % predicted forced expiratory volume in 1 second [FEV1] < 80% and FEV1/forced vital capacity [FVC] ratio < 70%) and a history of CV or cerebrovascular disease and/or significant CV risk factors.

Note: in this document

1. The term “double-blind treatment period” applies to the following 2 scenarios:
  - When used in “maximum of 36-months double-blind treatment period”
  - When used for patients who completed 36-months treatment (completer)
2. The term “during the treatment period” refers to on-treatment period.
3. The term “during the whole study period” refers to both on-treatment and off-treatment (post-treatment follow-up) periods.

The study consists of two-week washout/run-in period (for patients on a long-acting muscarinic antagonist [LAMA]) followed by a maximum of 36-month double-blind treatment period.

Signed informed consent form (ICF) from the patient or the patient’s legally authorized representative will be obtained before any study-related procedures are begun. All patients will be assigned a patient identification (PID) number via the interactive web response system (IWRS). Patients meeting the entry criteria for this study will be randomized (1:1) to acclidinium bromide 400 µg (abbreviated as acclidinium hereafter) twice a day (BID) or placebo BID. This study will conclude when 122 patients have experienced an adjudicated MACE.

Patients who prematurely discontinue investigational product (IP) will participate in a post-treatment follow-up period. The follow-up period will include on-site visits and telephone visits to collect MACE, COPD exacerbations, concomitant medications, and SAEs for the remainder of the study duration.

An independent Data Safety Monitoring Board (DSMB) will be established for this study. The DSMB will periodically monitor and review relevant clinical safety data, including adjudicated MACE.

Patients will be assessed according to the Schedule of Evaluations (See Section 2 of the clinical study protocol [CSP]).

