#### **4.2.2.3 Prior and concomitant medications**

The World Health Organization Drug Dictionary (WHO DD), enhanced version of March 2011 or newer, will be used to classify prior and concomitant medications by therapeutic class.

Prior medication is defined as any medication taken 15 days before signing ICF, regardless of stop date. Concomitant medication is defined as any medication taken during the treatment period between the date of the first dose of the double-blind IP and the date of the last dose of the double-blind IP, inclusive.

Prior and concomitant medications will be tabulated by the third level of Anatomical Therapeutic Chemical (ATC) classification code, preferred name, and treatment group.

All concomitant medications will be classified for each one of the two following periods and will be summarized by the third level of ATC classification code, preferred name, and treatment group (Analysis Population: FAS):

- 1) Medications that the patient started to take before the randomization and continued after the first double-blind IP administration, and
- 2) Medications that the patient started to take during the treatment period (from the first double-blind IP administration to the last double-blind IP administration).

In addition, medications that were used between the last double-blind IP administration and to the study end will be summarized by the third level of ATC classification code, preferred

name, and treatment group (Analysis Population: patients who discontinued the double-blind IP and entered into post-treatment follow-up period).

Number and percentage of patients who used any medication for COPD will be presented by therapeutic categories as follows (but not limited to) by treatment groups:

- Long-Acting  $\beta$ 2-Agonists (LABA)
- LAMA
- Short-Acting  $\beta$ 2-Agonists (SABA)
- Short-Acting Muscarinic Antagonist (SAMA)
- ICS
- LABA and ICS combination (free and fixed)
- LABA and LAMA combination
- SABA and SAMA combination
- Leukotriene modifiers
- Oral phosphodiesterase type 4 (PDE4)
- Systemic corticosteroid
- Oxygen
- Methylxanthines
- Influenza vaccine
- Pneumococcal vaccine

Specifically, medication in the reporting by therapeutic categories is presented for each of the two following periods:

- 1) Prior medication for COPD the patient is taken at the time of signing ICF, regardless of the onset or stop date , and

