- 2) Concomitant medication for COPD that the patient started to take before the randomization and continued after the first double-blind IP administration.

In addition, medications for COPD that were used between the last double-blind IP administration and to the study end will be summarized by therapeutic categories (Analysis Population: patients who discontinued the double-blind IP and entered into post-treatment follow-up period).

Multiple medications used by a patient will only be counted once.

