### **Subgroup analyses**

To evaluate the consistency in the primary efficacy endpoint over demographics and baseline characteristics, subgroup analyses will be performed. The subgroups are described below:

- Age group ( $\geq 40$  and  $< 60$  years,  $\geq 60$  and  $< 70$  years,  $\geq 70$  years old)
- Sex (Female, Male)
- Race (White, Other)
- Smoking status (Current smoker, Ex-smoker)
- Baseline ICS use (Yes, No)
- Baseline COPD severity (moderate, severe, and very severe)
- History of at least one exacerbation in the past year ( $0, \geq 1$ )

Exacerbation rate in aclidinium group will be compared to exacerbation rate in the placebo group for each subgroup (on-treatment analysis) using a negative binomial regression model. The response variable in the model will be the number of moderate or severe COPD exacerbations experienced by a patient during the first year of treatment. The model will include treatment group, each subgroup, and the interaction term. In order to adjust for the exposure for each patient, the natural logarithm of the exposure time (in years) during the first year of treatment (subtracting the time when a patient experienced COPD exacerbation) will be used as an offset variable.

The estimated treatment effect (i.e., the rate ratio of aclidinium over placebo) and corresponding 95% CI will be presented graphically.

In addition, the primary efficacy endpoint will be analyzed (on-treatment analysis) for the following 2 subgroups:

- LABA users (with and without ICS): include patients who took LABA and/or LABA/ICS during the treatment period.
- LABA/ICS users: include patients who took LABA/ICS during the treatment period.

That is, data for each subgroup will be extracted first, then do analysis on each set of data using the same approach as the corresponding primary analysis.

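### The LABA and LABA/ICS subgroups are defined by medication taken at any time on treatment, so the first-year rate ratio within them is not a randomized comparison

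*SAP*

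**What the plan says.** The subgroup text in SAP 4.2.4.1 first lists seven subgroups based on demographic or baseline factors. It then adds two more. LABA users "include patients who took LABA and/or LABA/ICS during the treatment period", and LABA/ICS users "include patients who took LABA/ICS during the treatment period". For both, "data for each subgroup will be extracted first, then do analysis on each set of data", using the primary model on the on-treatment exacerbation count of year 1.

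SAP 1.2 states that the phrase about the treatment period "refers to on-treatment period", within a "maximum of 36-month double-blind treatment period". SAP 4.2.2.3 gives the same span when it classifies medications: "Medications that the patient started to take during the treatment period (from the first double-blind IP administration to the last double-blind IP administration". SAP 4.2.3.2 lists the treatment period and the first year of treatment as two separate periods, so the phrase cannot be read as year 1 only.

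The SAP fixes its other medication factor before treatment: baseline ICS use (3.1.7.4) means use within 15 days before first dose. It also already separates pre-randomization COPD medication: "Concomitant medication for COPD that the patient started to take before the randomization and continued after the first double-blind IP administration".

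The two subgroup labels recur for FEV1 (4.2.4.3) and CAT (4.2.6.1) without a new definition, so the same one is implied there but not stated.

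**The concern.** Randomization protects a comparison within a subgroup only if membership is fixed before treatment can affect it. Here a patient may enter because LABA was started on study. Exacerbations, worsening symptoms and time on IP can all lead to such a start, and treatment may change each of them. A patient may also enter through LABA started in year 2 or 3, when the year-1 outcome is already complete.

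Patients already on LABA at first dose who continue are not the problem; those who start later are. The SAP does not limit membership to the former.

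At stake is how the result is read. A rate ratio from these subgroups would naturally be taken as the effect of aclidinium on top of LABA, as compared by randomization, and this definition does not support that reading. The absolute rates shown for the subgroup could also be inflated.

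**Working it through.** **Inputs from the SAP.** From 1.3.2: 4,000 patients, placebo rate 0.8 per year, rate ratio 0.86, k = 0.67, 30% treatment discontinuation in year 1. From 1.3.1: 40% discontinuation by year 2. From 1.2: 1:1 allocation, 36 months at most.

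**The SAP's own figure.** With 2,000 per arm and mean year-1 exposure 1 − 0.30/2 = 0.85 years (discontinuation spread evenly):

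- Var(log RR) = (1/2000)[1/(0.8×0.85) + 0.67 + 1/(0.688×0.85) + 0.67] = 4.521/2000 = 0.00226, SE 0.0475
- z = 0.1508/0.0475 − 1.96 = 1.21, power 88.7%

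This reproduces the stated figure of about 89%, so the inputs are a sound base.

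**Inputs that are assumed.** The SAP gives no LABA figures. Baseline use is taken as 30%, 50% or 70%, unrelated to the exacerbation rate. Start behaviour is varied in the scenarios below.

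**Model.** Exacerbations are Poisson with a gamma patient effect of variance 0.67. The discontinuation hazard is −ln(0.70) = 0.357 in year 1 and −ln(0.60/0.70) = 0.154 per year afterwards; carrying the latter into year 3 is an assumption. Members are baseline users plus anyone who starts LABA before stopping IP, up to 3 years. The ratio is year-1 on-treatment events over time in the subgroup, aclidinium over placebo. There are 1.5 million simulated patients per arm, with simulation error about ±0.004.

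| Scenario | Ratio at true 0.86 | Ratio at true 1 | Placebo rate in subgroup (true 0.80) | Placebo members qualifying only after year 1 |
|---|---|---|---|---|
| 1. Starts follow exacerbations, probability 0.1–0.5 per event, equal in both arms | 0.858–0.882 | 0.997–1.003 | 0.85–1.10 | 3–21% |
| 2. Starts unrelated to exacerbations, 5–30% per year | 0.857–0.863 | 0.996–1.003 | 0.80 | 2–24% |
| 3. Two-fold difference between arms in per-event start probability (illustration only) | 0.81–0.92 | 0.94–1.06 | – | – |
| Scenario 1 with membership fixed at baseline | 0.857–0.864 | 0.995–1.004 | 0.80 | none |

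**Mechanism in one case.** Take 30% baseline use, a 40% chance of starting after each exacerbation, and a constant 30% annual discontinuation. Then 55.0% of placebo and 52.8% of aclidinium patients become members. The placebo rate among members is 1.12 and the aclidinium rate 0.986, so the ratio is 0.986/1.119 = 0.881 at a true 0.86. Patients prone to exacerbations are drawn in, and slightly fewer of them in the arm with the lower rate.

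**Scale.** If half of each arm (1,000 patients) were members, Var(log RR) = 4.521/1000, SE 0.067, and the 95% CI around 0.86 is about 0.75 to 0.98. The largest shift in scenario 1, 0.022, is just under a tenth of that width of 0.23.

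**The case against.** The strongest reply is that little follows in practice. With equal start behaviour the ratio moves by at most about 0.02 toward 1, and no spurious benefit appears when there is no true effect. Late qualification alone does no harm: in scenario 2 up to 24% of members qualify only after year 1 and the ratio does not move. If the protocol bars or limits LABA starts on study, the subgroup as written nearly coincides with a baseline one. SAP 2.2.1 refers to disallowed medications without listing them, so this cannot be settled here. The two subgroups are introduced after the baseline list, lie outside the test sequence in 4.2.4, and are never called confirmatory. Larger shifts appear only in scenario 3, and nothing in the SAP supports a difference in start behaviour between arms.

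All of this stands as a limit on size. It does not rescue the definition. The SAP does not show that late starts are rare, and it has a separate category for medication begun on treatment. The section's stated aim is consistency over demographic and baseline characteristics, which these two subgroups do not satisfy. If late starts are rare, a baseline flag costs almost nothing.

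For FEV1 and CAT the post-randomization selection is the same, but those outcomes run to Visit 12 or the end-of-treatment visit. The argument about a closed year-1 window does not carry over, and no size was calculated for them.

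**Conclusion.** The point holds and is minor. As written, both subgroups are selected on post-randomization medication over up to 36 months for a year-1 outcome, so the ratio within them is not a randomized comparison once any patient qualifies through a later start.

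The effect on the ratio is probably small if both arms start LABA in the same way. The more visible distortion would be in the absolute rates, and only if starts follow exacerbations. Both statements rest on the assumed LABA use and start rates; the SAP fixes neither the size nor the direction of the bias. The primary efficacy analysis, its power and the MACE analysis are not touched.

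**What to change.** Define both subgroups by LABA (or LABA/ICS) use in place at first dose, using the existing category in SAP 4.2.2.3: "Concomitant medication for COPD that the patient started to take before the randomization and continued after the first double-blind IP administration". The baseline ICS rule in 3.1.7.4 is an alternative precedent, since it too is fixed before treatment. Apply the same flag to the FEV1 and CAT subgroups and say so there.

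State how uncertain start dates are treated for this flag. Under SAP 3.1.5.8 a partial start date in the year or month of first dose is set to the first-dose date, which would fail a test of having started before randomization; wholly missing dates are not covered. This is not an error in the current definition, but it would affect the new one. Such a date should not by itself exclude a patient whose use falls under "Prior medication for COPD the patient is taken at the time of signing ICF, regardless of the onset or stop date" and was not stopped before first dose.

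If use during treatment is the question of interest, keep that version as a second analysis labelled exploratory and non-randomized, and tabulate new LABA starts by arm.

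The cost is a short text change and one derived flag from medication records already collected. The subgroups would become smaller by an amount the SAP does not allow to be estimated.

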#### **4.2.4.2 Secondary efficacy variable**

The secondary efficacy endpoint of rate of hospitalizations due to COPD exacerbations per patient per year during the first year of treatment will be analyzed (on-treatment analysis) using the same model as for the analyses of the primary efficacy endpoint, including on-study analysis as sensitivity analysis.

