#### **3.1.6 Definition of COPD exacerbations**

The onset and end of a COPD exacerbation is defined by the investigators in their assessment of patient symptoms and initiation/finalization of treatment (as defined below for the severity of exacerbation), and recorded on COPD Exacerbation page of electronic case report forms (eCRFs).

The severity of a COPD exacerbation is assessed according to the following scale:

- Mild: Increase in COPD symptoms (e.g., dyspnea, cough, sputum volume, sputum purulence) during at least 2 consecutive days, managed by the patient at home by increasing short-acting bronchodilator and/or inhaled corticosteroid (ICS) use
- Moderate: Increase in COPD symptoms (e.g., dyspnea, cough, sputum volume, sputum purulence) during at least 2 consecutive days that does not lead to hospitalization but is treated with antibiotics and/or systemic corticosteroids

- Severe: Increase in COPD symptoms (e.g., dyspnea, cough, sputum volume, sputum purulence) during at least 2 consecutive days that leads to hospitalization (overnight stay at hospital or emergency room) or death

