### Definitions of New and/or Relapsed COPD exacerbations

The interval between 2 consecutive COPD exacerbations must be at least 7 days. Therefore, if 2 COPD exacerbations occur within 7 days of each other, then they will be considered as 1 event (i.e., the second one is considered as a relapse). Inpatient hospitalization due to COPD occurring during an exacerbation should not be regarded as a new exacerbation. In order to be counted as a new exacerbation it must be preceded by at least 7 days in which none of the exacerbation criteria is fulfilled.

A COPD exacerbation will be derived as a new COPD exacerbation if and only if either of the following conditions is met:

- The exacerbation is the first episode, or
- The start date of the exacerbation is greater than or equal to 7 days since the previous exacerbation

All reported exacerbations will be combined with any reported relapses. Relapses will be considered as a continuation of the previous event. That is, the onset of exacerbation event will be the same as the onset of first exacerbation event with a resolution date being derived as the resolution date of last relapse. The severity of exacerbation event derived in this way will be the most severe of first exacerbation or any derived relapse.

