#### 4.2.4.1 Primary efficacy outcome variable

The primary efficacy variable is rate of moderate or severe COPD exacerbation per patient per year during the first year of treatment. The primary analysis (on-treatment analysis) is to compare rate of moderate or severe COPD exacerbation per patient per year during the first year of treatment between aclidinium and placebo in patients in the FAS. Patients will be analyzed according to randomized treatment.

The null hypothesis is that the exacerbation rate on aclidinium is equal to the exacerbation rate on placebo. The alternative hypothesis is that the exacerbation rate on aclidinium is not equal to the exacerbation rate on placebo, i.e.:

$$H_0: \text{Rate ratio (aclidinium over Placebo)} = 1$$

versus

$$H_a: \text{Rate ratio (aclidinium over Placebo)} \neq 1$$

Exacerbation rate in aclidinium group will be compared to exacerbation rate in the placebo group using a negative binomial regression model. The response variable in the model will be the number of moderate or severe COPD exacerbations experienced by a patient during the first year of treatment. The model will include treatment group, baseline ICS use, baseline COPD severity, history of at least one exacerbation in the past year, and smoking status as factors. In order to adjust for the exposure for each patient, the natural logarithm of the exposure time (in years) during the first year of treatment will be used as an offset variable. When used as the offset variable, the exposure time will be adjusted by subtracting the time when a patient experienced COPD exacerbation(s) (i.e., not at risk during an exacerbation). The model is as follows:

*Number of moderate or severe exacerbations during the first year of treatment = treatment group + baseline ICS use + baseline COPD severity + history of at least one exacerbation in the past year + smoking status*

The estimated treatment effect (i.e., the rate ratio of aclidinium over placebo), corresponding 95% CI, and two-sided p-value for the rate ratio will be presented. In addition, the exacerbation rate and the corresponding 95% CI within each treatment group will be presented.

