If the Negative Binomial regression model does not converge, the Poisson regression model with robust variance estimate using sandwich method will be applied. A scale parameter will be included to take overdispersion into account in fitting Poisson regression model. This would be a similar SAS GENMOD model to the one used for the Negative Binomial, but will specify Poisson as the distribution and include a scale parameter (DSCALE).

The primary analysis on the primary efficacy endpoint will be based on on-treatment analysis. For those patients who prematurely discontinue IP during the first year of treatment and have follow-up assessments, the primary analysis described above will be based on the data (events) collected before treatment discontinuation.

The secondary analysis on the primary efficacy endpoint will be based on on-study analysis using the same model as for the primary analyses of the primary efficacy endpoint. For those patients who prematurely discontinue IP during the first year of treatment and have follow-up assessments, the secondary analysis will include the events collected during the PTFU period up to one year.

The individual exacerbation criteria (use of systemic corticosteroids, use of antibiotics, and inpatient hospitalization due to COPD) will also be analysed using the same method as the primary analysis for on-treatment analysis during the first year of treatment, and will be summarized descriptively for on-study analysis over the whole study period.

The frequency of events and descriptive statistics of moderate or severe COPD exacerbations will also be provided by analysis method and period:

- On-treatment analysis during the first year of treatment
- On-study analysis during the first year of treatment
- On-treatment analysis over the whole study period
- On-study analysis over the whole study period.

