### **Analyses for COPD Exacerbations**

The rate of COPD exacerbations per patient per year (any, and moderate or severe) and rate of hospitalizations due to COPD exacerbations per patient per year will be analyzed using a Negative Binomial regression model (or Poisson regression model taking overdispersion into account for analyses that Negative Binomial regression does not converge) similar to the primary analysis of the primary efficacy variable. The exposure time will be re-calculated based on the last data collection during the whole study period.

The number of patients with at least one COPD exacerbation (any, mild, moderate, severe, and moderate or severe) will be analyzed based on a logistic regression model with treatment group, baseline ICS use, baseline COPD severity, history of at least one exacerbation in the past year, and smoking status as factors. The estimated treatment effect (i.e., the odds ratio of aclidinium over placebo), corresponding 95% CI, and two-sided p-value for the odds ratio will be presented. The model is as follows:

*Response (Yes=1/No=0) = treatment group + baseline ICS use + baseline COPD severity + history of at least one exacerbation in the past year + smoking status*

Time (in days) to first COPD exacerbation (any, and moderate or severe), time (in days) to second COPD exacerbation (any, and moderate or severe), time (in days) to third COPD exacerbation (any, and moderate or severe), time (in days) to first hospitalization due to COPD exacerbation, and time (in days) to withdrawal of the double-blind IP due to COPD exacerbation will be analyzed by means of Kaplan-Meier estimators and Cox Proportional Hazards model. The estimates of the hazard ratio comparing aclidinium with placebo will be derived using the Cox proportional hazard model for the time in terms of the number of days served as a response variable and treatment group, baseline ICS use, baseline COPD severity, history of at least one exacerbation in the past year, and smoking status as factors. The hazard ratio (aclidinium over placebo), corresponding 95% CI, and two-sided p-value for the hazard ratio will be presented. The model is as follows:

*Survival time = treatment group + baseline ICS use + baseline COPD severity + history of at least one exacerbation in the past year + smoking status*

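### The hospitalization-rate model takes over an offset that removes time in exacerbation as not at risk, although COPD admissions arise during exacerbations; modelled rates come out roughly 2–7% too high and the rate ratio moves by less than 1%

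*SAP*

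**What the plan says.** Section 4.2.4.1 fits a negative binomial model to the number of moderate or severe exacerbations in year 1. As offset, "the natural logarithm of the exposure time (in years) during the first year of treatment will be used as an offset variable", and it is then modified: "the exposure time will be adjusted by subtracting the time when a patient experienced COPD exacerbation(s) (i.e., not at risk during an exacerbation").

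Section 4.2.4.2 carries this model to the only secondary efficacy endpoint, the hospitalization rate, "using the same model as for the analyses of the primary efficacy endpoint", with an on-study version for sensitivity. It gives no separate offset. Section 4.2.4.3 analyses the whole-study hospitalization rate with a model "similar to the primary analysis of the primary efficacy variable. The exposure time will be re-calculated based on the last data collection during the whole" of the study. Exposure changes there only to cover the longer period, so the same offset appears to be inherited, although the word used is similar rather than same.

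Three other places matter:

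- Section 3.1.6 defines a severe exacerbation as increased symptoms "during at least 2 consecutive days that leads to hospitalization (overnight stay at hospital or emergency room) or death". Its rules on new and relapsed events add: "Inpatient hospitalization due to COPD occurring during an exacerbation should not be regarded as a new exacerbation".
- Section 3.3 names the hospitalization itself as the event and sends the reader to the general rate formula in 3.1.7.1. That formula divides by the whole time from randomization to the follow-up date, with nothing removed.
- Section 3.4.1.9 gives each hospitalization its own onset and end date.

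**The concern.** Subtracting time in exacerbation is sound when the counted event is a new exacerbation: a patient already in an episode cannot start another until 7 days free of the criteria have passed. For hospitalization the logic turns round. The symptoms come first and lead to the admission, and the SAP foresees admission during an episode already under way. The model therefore counts events that fall in the time its denominator leaves out.

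An invented example: onset on day 100, antibiotics on day 102, admission on day 106, resolution on day 121. The admission is counted, but days 100 to 121 are removed, including the days on which admission was most likely.

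Two things are at stake. The modelled hospitalization rates per arm are too high, and they will not agree with the descriptive rates for the same endpoint. In addition, the denominator depends on a post-randomization quantity that treatment is meant to change, so the rate ratio can move. The endpoint is the last step of the testing sequence in section 4.2.4.

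**Working it through.** **Inputs from the SAP (section 1.3.2; 1:1 allocation from 1.2).** 4,000 patients, so 2,000 per arm; placebo rate 0.8 per year; rate ratio 0.86, so aclidinium rate 0.8 × 0.86 = 0.688; k = 0.67; 30% treatment discontinuation in year 1; two-sided 5% level. Stated power: about 89%.

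**Assumptions, not in the SAP.** Mean exacerbation duration D of 10 to 30 days, equal in both arms unless stated. Where a hospitalization rate is needed, 20% of placebo exacerbations lead to admission, giving 0.8 × 0.20 = 0.16 per year.

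**1. Reproducing the stated power.** With mean exposure 0.85 years (uniform discontinuation):

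Var(log RR) = [1/(0.85 × 0.8) + 0.67 + 1/(0.85 × 0.688) + 0.67] / 2000 = 4.521/2000 = 0.00226, so SE = 0.0475.

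z = |ln 0.86| / 0.0475 − 1.96 = 3.17 − 1.96 = 1.21, which gives 88.7% power. Exponential discontinuation (mean exposure 0.841) gives 88.5%. The stated figure reproduces, so the inputs are read correctly.

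**2. Time removed and overstatement.** Share removed s = rate × D / 365.25. Overstatement of the arm's rate = 1/(1 − s) − 1. Multiplier of the rate ratio = (1 − s for placebo) / (1 − s for aclidinium).

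| D (days) | Removed, placebo | Removed, aclidinium | Overstated, placebo | Overstated, aclidinium | Multiplier |
|---|---|---|---|---|---|
| 10 | 2.19% | 1.88% | 2.24% | 1.92% | 0.9969 |
| 14 | 3.07% | 2.64% | 3.16% | 2.71% | 0.9956 |
| 21 | 4.60% | 3.96% | 4.82% | 4.12% | 0.9933 |
| 30 | 6.57% | 5.65% | 7.03% | 5.99% | 0.9902 |

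A true ratio of 0.86 would be estimated as 0.857 (10 days) to 0.852 (30 days).

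**3. Check by simulation.** Negative binomial models with both offsets were fitted to simulated data (400,000 patients per scenario, exponential discontinuation, hospitalized episodes 1.5 times as long as the others). For D of 10, 14 and 21 days the placebo hospitalization rate was overstated by about 2.5%, 3.5% and 5.3%, and the ratio was multiplied by about 0.996, 0.995 and 0.993. With no effect on exacerbations the multiplier was 1.000 to within simulation error, while both arms' rates were still overstated by 2.5–5.4%.

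**4. What sets the direction.** The multiplier depends on count × duration. Placebo at 0.8 × 14 = 11.2 days per year equals aclidinium at 0.688 × 16.3 = 11.2 days: multiplier 1.000. With 17 days on aclidinium it is (1 − 11.2/365.25) / (1 − 11.7/365.25) = 1.001, slightly against aclidinium.

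**5. Consequence for the test.** Take exacerbations reduced by 14% and no true effect on hospitalization:

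SE(log RR) = √{2 × [1/(0.85 × 0.16) + 0.67] / 2000} = 0.090.

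The multipliers in step 2 are shifts of 0.0031/0.090 = 0.03 SE (10 days) to 0.0098/0.090 = 0.11 SE (30 days). Two-sided type I error moves from 5.00% to between 5.01% and 5.14%.

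**The case against.** **Each admission could be read as one severe exacerbation.** The event would then begin at an exacerbation onset, and a patient already in an episode could not start another, so the offset would be right. This does not match the SAP: section 3.3 counts hospitalizations, section 3.4.1.9 dates each one separately, and relapses are merged into one long episode in which a late or repeat admission can still occur.

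**The arithmetic is not specific to hospitalization.** The same shares of time are removed in the primary model. That is true; step 2 measures the gap between a rate per reduced time and a rate per full follow-up time. For exacerbation counts the gap has a stated and valid reason. For admissions it has none.

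**A reader might infer that the offset always favours aclidinium once exacerbations are reduced.** The documents do not support this. Fewer but longer episodes can leave total time equal or higher, as step 4 shows, and the SAP gives no durations.

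**A reader might extend the point to the separate exacerbation criteria in section 4.2.4.1**, which "will also be analysed using the same method as the primary analysis for on-treatment analysis during the first year of treatment". These can naturally be read as exacerbations meeting each criterion. On that reading they are exacerbation counts and the subtraction should stay, so the point is not pressed there.

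**Full follow-up time is itself a convention**, since it includes inpatient days on which no new admission can occur. This stands, but it is the convention the SAP already uses in 3.1.7.1.

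**Conclusion.** The reason given for the offset does not hold for the hospitalization endpoint, and section 4.2.4.2 applies it there without comment. For the whole-study rate in 4.2.4.3 the inheritance is probable rather than explicit. Relative to the SAP's own rate definition, the overstatement occurs whenever time in exacerbation is subtracted, and needs no treatment effect. Its size, about 2–7%, rests on the assumed durations.

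The shift in the rate ratio is a separate and conditional effect: below 1% over the range examined, towards aclidinium only if total time in exacerbation is lower on aclidinium, and absent if that time is equal. It could matter only for a borderline result. This is a minor correction to the plan and does not threaten the endpoint's conclusion.

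**What to change.** In section 4.2.4.2, and for the hospitalization rate in 4.2.4.3, state that the offset is the log of full follow-up time in the analysis window (on-treatment or on-study, as applicable), in line with 3.1.7.1 and without subtracting time in exacerbation. Keep the subtraction for models that count exacerbations, including the criteria in 4.2.4.1 where these are counted as exacerbations meeting each criterion.

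The cost is one sentence and one offset variable, with no new data. The modelled hospitalization rates would be a few percent lower, and the rate ratio may be marginally less favourable to aclidinium.
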